6.1.3.1. Maintenance Primary Population

Unless otherwise specified, treatment comparisons of categorical efficacy and health outcomes variables will be analyzed using CMH test with treatment group and covariates as mentioned in Section 6.3 in the model. The CMH p-value will be reported, and the CMH adjusted odds ratio along with the 95% two-sided asymptotic (that is, not continuity corrected) CIs.

Each continuous efficacy and health outcomes measure score, change from baseline and percent improvement from baseline will be summarized by treatment group at all scheduled visits during Maintenance Period including Week 52, using descriptive statistics (n, mean, standard deviation (SD), median, minimum, and maximum).

Treatment comparisons for continuous efficacy and health outcome variables will be made using ANCOVA model as specified.

When the ANCOVA is used, the model will include treatment, baseline value and covariates as mentioned in Section 6.3. The ANCOVA analysis will be conducted as described in Section 6.1.2.

The KM product limit method will be used to estimate the survival for time to event analyses (e.g., time to loss of IGA response or time to loss of EASI-50 or time to loss of EASI-75). The stratified log-rank test will be performed with treatment group and covariates as mentioned in Section 6.3 in the model. A KM plot of the time to event by treatment group may be provided.

Unless specified otherwise, Fisher's exact test will be used for AEs and other categorical safety measures. Odds ratios will be created with lebrikizumab treatment as the numerator and placebo

as the denominator. Continuous vital sign and laboratory values will be analyzed by an ANCOVA model with treatment and baseline value as independent variables.

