5.1.3. Maintenance Period (Week 16 to Week 52 [36 Weeks])

5.1.3.1. Maintenance Blinded Period

After completion of the Week 16 visit, patients who have responded to treatment (defined as having an IGA of 0 or 1 or a 75% reduction in EASI from Baseline to Week 16 [EASI-75] according to IWRS system) will enter the Maintenance Period and will be re-randomized 2:2:1 to one of the following treatment groups: lebrikizumab 250 mg Q2W, lebrikizumab 250 mg Q4W, or placebo Q2W. Throughout the maintenance blinded period, patients will receive placebo, as appropriate, to maintain the study blind across treatment groups.

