5.2. Determination of Sample Size

For FDA: In the DRM06-AD01 Phase 2b study (J2T-DM-KGAF), the proportion of patients who achieved an IGA score of 0 or 1 at Week 16 using the rescue medication non-response sensitivity analysis was approximately 34.7% for lebrikizumab 250 mg Q2W versus 7.7% for placebo. A sample size of 96 for lebrikizumab 250 mg Q2W versus 48 for placebo will have more than 95% power to detect a statistically significant difference based on a two group continuity corrected chi-square test with a two-sided significance level of 0.05. However, to ensure sufficient safety information is collected and to ensure sufficient responders for the Maintenance Period, the sample size will be increased to approximately 400 in total with a randomization ratio of 2:1 lebrikizumab:placebo.

For European Medicines Agency (EMA): In the DRM06-AD01 Phase 2b study (J2T-DM-KGAF), the proportion of patients who achieved an IGA score of 0 or 1 at Week 16 using the rescue medication non-response sensitivity analysis was approximately 34.7% for lebrikizumab 250 mg Q2W versus 7.7% for placebo, and the proportion of patients who achieved an EASI-75 at Week 16 using the rescue medication non-response sensitivity analysis was approximately

48.0% for lebrikizumab 250 mg Q2W versus 11.5% for placebo. A sample size of 96 for lebrikizumab 250 mg Q2W versus 48 for placebo will have more than 95% power to detect a statistically significant difference based on a two group continuity corrected chi-square test with a two-sided significance level of 0.05 for each of the co-primary endpoints, which imply and overall power of at least 90%. However, to ensure sufficient safety information is collected and to ensure sufficient responders for the Maintenance Period, the sample size will be increased to 400 in total with a randomization ratio of 2:1 lebrikizumab:placebo.

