6.1. General Considerations

Statistical analysis of this study will be the responsibility of Eli Lilly and Company (Lilly). The latest version of the Medical Dictionary for Regulatory Activities (MedDRA) will be used.

Analyses and summaries from assessment of endpoints described in the protocol (for example, described in KGAB Protocol Table 1) are planned to be included in a clinical study report (CSR). Analyses and summaries for key safety data are also planned to be included in the CSR. Results from additional efficacy analysis and other safety analyses may also be provided in the CSR as deemed appropriate.

Any change to the data analysis methods described in the protocol will require a protocol amendment ONLY if it changes a principal feature of the protocol. Any other change to the data analysis methods described in the protocol and the justification for making the change will be described in the CSR.

All statistical processing will be performed using SAS® unless otherwise stated. Some of the analyses described in this document will be incorporated into interactive display tools instead of or in addition to static displays. Except where noted, all statistical tests will be two-sided and will be performed at the 0.05 level of significance.

The Schedule of Visits and Procedures outlined in the protocol specifies the allowable windows for assessments. Assessments performed outside these windows will not be excluded from any analysis, unless specified otherwise.

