For assessments of the primary endpoints and other binary efficacy and health outcomes endpoints, the following will be provided:

- Crude proportions for each treatment group along with the 95% two-sided asymptotic (that is, not continuity corrected) confidence intervals (CIs) will be provided.

- The estimated common risk difference along with 95% CIs. The common risk difference is the difference in proportions adjusted for the stratification factors as mentioned in Section 6.3. SAS® PROC FREQ will be used for the estimates and CIs, where the CIs are calculated by using Mantel-Haenszel-Sato method (Sato 1989).
- Cochran-Mantel-Haenszel (CMH) test will be used to compare the treatment groups while adjusting for the stratification factors. The CMH p-value will be reported, and the CMH adjusted odds ratio along with the 95% two-sided asymptotic (that is, not continuity corrected) CIs.

Treatment comparisons of key continuous efficacy variables and health outcome variables at each postbaseline time point will be made using analysis of covariance (ANCOVA) with the following in the model: treatment group, baseline value, and stratification factors mentioned in Section 6.3. Type III tests for least squares (LS) means will be used for statistical comparison between treatment groups. The LS mean difference, standard error, p-value, and 95% CI, unless otherwise specified, will also be reported.

Treatment comparisons of other continuous efficacy variables and health outcome variables with multiple postbaseline measurements will be made using mixed-model for repeated measures (MMRM). When MMRM is used, the model includes treatment, baseline value, visit, the interaction of the baseline value-by-visit, the interaction of treatment-by-visit, and the stratification factors mentioned in Section 6.3 as fixed factors. The covariance structure to model the within-patient errors will be unstructured. If the unstructured covariance matrix results in a lack of convergence, the heterogeneous Toeplitz covariance structure, followed by the heterogeneous autoregressive covariance structure will be used. The restricted maximum likelihood (REML) will be used. The Kenward-Roger method will be used to estimate the denominator degrees of freedom. Type III tests for the LS means will be used for the statistical comparison; the 95% CI will also be reported.

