6.2.2.4. Maintenance Supportive Estimand for Continuous Endpoints (Hypothetical)

The maintenance supportive estimand for continuous endpoints only is a hypothetical estimand representing the clinical question of interest: what is the difference between treatment conditions, i.e., Lebrikizumab vs Placebo, in the target patient population, in means after 52 weeks if rescue medication was not available and all patients adhered to the treatment and did not transfer to escape arm?

The maintenance supportive estimand for continuous endpoints is described by the following attributes:

- A. Population: Maintenance Primary Population as described in Section 6.1.1.
- B. Endpoint: apply to all major and other secondary continuous endpoints for Maintenance Period
- C. How to account for intercurrent events (ICEs)
 - a. For subjects who require any use of rescue medication, discontinue treatment after week 16, or transfer to escape arm, a hypothetical strategy will be used to estimate what the treatment effect would have been if rescue medication was not available and all subjects adhered to the treatment and did not transfer to escape arm. Therefore, hypothetical strategy is used for these types of ICEs.
- D. Population-level summary: difference in means between treatment conditions

Analytical details on how missing data including those as a result of intercurrent events will be handled for Maintenance Period can be found in Section 6.4.2. Detailed analyses relative to

estimands including analysis type, method and imputation, population, time point, and treatment comparisons for efficacy/health outcomes analyses can be found in Section 6.11.

The following table (Table KGAB.6.4) summarizes the analytical strategies that will be conducted on the intercurrent events for the four maintenance estimands.

Table KGAB.6.4. Analysis of Primary and Supportive Estimands for Maintenance Period

Maintenance Estimand	Analysis Strategy for Intercurrent Events				Transfer to escape arm	Missing Data Imputation Method
	Rescue Medication		Treatment Discontinuation			
	Topical rescue medication	Systemic rescue medication	Due to lack of efficacy	Due to any other reasons		
Maintenance Primary Estimand (Hybrid)	Hypothetical: Set to missing	Composite: Set to baseline	Composite: Set to baseline	Hypothetical: Set to missing	Composite: Set to baseline	MCMC-MI

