A separate set of major secondary endpoints will be considered at Week 52 (End of Maintenance). These secondary endpoints across the 2 different regimens will be tested following the hierarchical testing procedure with a pre-specified order, that is, inferential conclusions about secondary endpoints require statistical significance at the 0.05 significance level.

The hierarchy for the major secondary endpoints at Week 52 is as follows

Q2W Maintenance therapy:

- Percentage of patients from those re-randomized to Q2W maintenance therapy having achieved EASI-75 at Week 16 who continue to exhibit EASI-75 at Week 52 (EASI-75 calculated relative to baseline EASI score).
- Percentage of patients from those re-randomized to Q2W maintenance therapy having achieved IGA 0 or 1 and a ≥ 2 -point improvement from Baseline at Week 16 who continue to exhibit an IGA 0 or 1 and a ≥ 2 -point improvement from Baseline at Week 52.

- Percentage of patients from those with a Pruritus NRS of ≥ 4 -points at baseline and re-randomized to Q2W maintenance therapy having achieved ≥ 4 -point reduction from baseline at Week 16 who continue to exhibit ≥ 4 -point reduction from baseline at Week 52.

Q4W Maintenance therapy:

- Percentage of patients from those re-randomized to Q4W maintenance therapy having achieved EASI-75 at Week 16 who continue to exhibit EASI-75 at Week 52 (EASI-75 calculated relative to baseline EASI score).
- Percentage of patients from those re-randomized to Q4W maintenance therapy having achieved IGA 0 or 1 and a ≥ 2 -point improvement from Baseline at Week 16 who continue to exhibit an IGA 0 or 1 and a ≥ 2 -point improvement from Baseline at Week 52.
- Percentage of patients from those with a Pruritus NRS of ≥ 4 -points at baseline and re-randomized to Q4W maintenance therapy having achieved ≥ 4 -point reduction from baseline at Week 16 who continue to exhibit ≥ 4 -point reduction from baseline at Week 52.

Q2W Maintenance therapy:

- Percentage change in EASI score from baseline at Week 52 for those patients re-randomized to Q2W maintenance therapy at Week 16.

Q4W Maintenance therapy:

- Percentage change in EASI score from baseline at Week 52 for those patients re-randomized to Q4W maintenance therapy at Week 16.

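### The Week 52 EASI percent-change ANCOVA names no variance structure; with a pooled variance, its 95% CI is too narrow if the small withdrawal-placebo arm fails moderately more often than lebrikizumab

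*SAP*

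**What the plan says.** **Model.** SAP 6.1.3.1 (Maintenance Primary Population) says "When the ANCOVA is used, the model will include treatment, baseline value and covariates as mentioned in Section 6.3". Section 6.3 supplies geographic region as the maintenance covariate. The analysis is run as in 6.1.2, which adds "The LS mean difference, standard error, p-value, and 95% CI, unless otherwise specified, will also be reported". Section 6.1.2 names a covariance structure and a degrees-of-freedom method only for the MMRM. For the ANCOVA it names neither, and no unequal-variance or robust option appears in 6.1.2, 6.1.3.1 or 6.4.2.1.

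**Outcome rule.** In Table KGAB.6.4 the maintenance primary estimand handles systemic rescue, discontinuation for lack of efficacy and transfer to escape by "Composite: Set to baseline". For percent change in EASI that value is 0%.

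**Allocation.** Week 16 responders are "re-randomized 2:2:1 to one of the following treatment groups" (SAP 5.1.3.1), in the order Q2W, Q4W, placebo. Table KGAB.6.2 lists each lebrikizumab regimen against placebo but does not say whether the three arms share one model.

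**Status.** SAP 6.6.2 puts "Percentage change in EASI score from baseline at Week 52 for those patients re-randomized to Q2W maintenance therapy at Week 16" seventh in the EMA maintenance hierarchy, with the Q4W counterpart eighth. Version 4 of the SAP made this a major secondary endpoint for EMA.

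**The concern.** An ordinary ANCOVA estimates one residual variance from all arms it is fitted to. That is safe when the arms are equally variable, and also when they are equally large in a two-arm fit. Here neither can be assumed.

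The analysed patients were Week 16 lebrikizumab responders, and a patient escapes on losing EASI-50 at Week 24, 32, 40 or 48. Those who stay in the blinded arms therefore sit well below 0% change, while every composite failure is placed at exactly 0%. The gap between the two clusters dominates the arm variance. If withdrawal placebo fails more often, which is the effect the comparison is meant to detect, the smallest arm will usually be the most variable. The larger and less variable lebrikizumab arms then set the error variance, and the standard error of the placebo contrast comes out too small. PROC MIANALYZE averages the within-imputation variances and so carries the shortfall through.

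At stake are the reported standard error, CI and p-value for two alpha-controlled EMA comparisons.

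**Working it through.** **Inputs from the documents**
- Two-sided 0.05 (SAP 6.1), so a nominal 95% CI.
- Sample size "increased to 400 in total with a randomization ratio of 2:1 lebrikizumab:placebo" (SAP 5.2): 400 x 2/3 = 267 on lebrikizumab.
- Planning EASI-75 rate on lebrikizumab 48.0% (SAP 5.2): 267 x 0.48 = 128 re-randomised responders. At 2:2:1 this is about 51:51:26.

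**Assumed, because the documents give no figure**
- Failure share q at Week 52 in each arm.
- Continuing responders at a mean of about -80 to -90%, SD 8-12. The worked example uses -88% and SD 10 in every arm.

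**The plan's own figures.** The only sizing figure is more than 95% power for 96 vs 48. The continuity-corrected formula gives 95.2% for IGA (95.5% by exact enumeration) and 99.6% for EASI-75, so it reproduces. No figure is given for Week 52. The nominal 95% also reproduces when arm variances are equal: 95.0% by formula and 95.1% in 6,000 simulated trials.

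**Formulas** (L = lebrikizumab, P = placebo)
- Arm variance: v(q) = (1-q) x 10² + q(1-q) x 88²
- Joint pooled variance: s² = (50 v_L + 50 v_L + 25 v_P) / 125
- Model SE = √[s² (1/51 + 1/26)]
- True SE = √[v_L/51 + v_P/26]
- Coverage = 2Φ(1.96 x model SE / true SE) - 1

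**Failure 5% vs 30%**
- v(0.05) = 95 + 0.0475 x 7744 = 462.8
- v(0.30) = 70 + 0.21 x 7744 = 1696.2
- s² = (100 x 462.8 + 25 x 1696.2) / 125 = 709.5
- Model SE = √(709.5 x 0.05807) = 6.42
- True SE = √(9.08 + 65.24) = 8.62
- Coverage = 2Φ(1.96 x 6.42/8.62) - 1 = 85.6%
- Pairwise fit: s² = (50 x 462.8 + 25 x 1696.2) / 75 = 874.0, model SE 7.12, coverage 89.5%

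**Failure 10% vs 30%.** v(0.10) = 787.0 and s² = 968.8, so model SE is 7.50 against a true 8.98, and joint coverage is 89.8%.

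**Failure 30% vs 60%.** v(0.60) = 40 + 0.24 x 7744 = 1898.6, close to v(0.30). Here s² = 1736.7, so model SE is 10.04 against 10.31, and coverage is 94.4%.

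**Simulation** of the full model (treatment, baseline EASI, region) at 51:51:26:

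| Failure, lebrikizumab / placebo | Joint fit | Pairwise fit | Joint fit, HC3 |
|---|---|---|---|
| 2% / 20% | 83.2% | 88.4% | 94.1% |
| 5% / 20% | 89.2% | 90.8% | 94.6% |
| 5% / 30% | 86.9% | 89.5% | 94.8% |
| 5% / 50% | 84.6% | 89.9% | 94.4% |
| 10% / 20% | 92.9% | 93.1% | 94.8% |
| 10% / 30% | 91.4% | 92.6% | 94.9% |
| 10% / 50% | 89.6% | 91.4% | 94.7% |
| 15% / 30% | 93.1% | 94.0% | 95.2% |
| 15% / 50% | 92.1% | 92.6% | 95.0% |
| 30% / 60% | 95.0% | 95.3% | 94.9% |
| 20% / 80% | 95.8% | 95.3% | 94.2% |

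In a separate check, arm-specific residual variances gave 93-95%.

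**Arm size** hardly matters. At 10% vs 30% the formula gives 89.9%, 89.8% and 89.7% for 37:37:19, 51:51:26 and 64:64:32.

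**Multiple imputation** does not repair it. With 25 within-arm imputations, Rubin's rules, and 10% then 20% missing, joint coverage was 87.1% and 86.0% (5% vs 30%), 85.0% and 87.6% (5% vs 50%), and 90.6% and 92.1% (10% vs 30%). Simulation error is about 1.3 points.

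**The case against.** Three stronger readings are tempting, and the documents support none of them.

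1. *The interval is known to cover only 85-93%.* The documents give no Week 52 failure rate, SD or arm variance. Both the pooled variance and the joint fit are inferred from silence. The pooled variance is the natural reading of an ANCOVA, but pairwise fitting is equally compatible with Table KGAB.6.2 and is milder.
2. *The composite rule makes placebo the most variable arm.* It does not. Since q(1-q) peaks at one half, placebo is more variable only when its failure share is nearer 50% than that of the active arms. At 30% vs 60% or 20% vs 80% there is little or no shortfall.
3. *The narrow interval inflates false positives.* If all arms share one distribution their variances are equal and the test keeps its level. Extra rejections when lebrikizumab truly works are not type I errors.

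The hierarchy also limits the consequence. These tests are reached only after six binary tests succeed. In a simulation imposing only the two EASI-75 tests, trials that passed both, and in which the pooled ANCOVA for Q2W was significant but HC3 was not, made up 0.5-1.7% of all trials. The other four tests can only lower that. The endpoint is not multiplicity-controlled for FDA.

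There are further cushions. Arm-level SDs will be reported, so unequal variances will be visible. The binary endpoints use CMH, which has no residual variance. A supplementary LOCF ANCOVA omits the set-to-baseline rule, but it answers a hypothetical question and does not correct the primary interval.

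These points reduce the importance of the concern. They do not supply the missing variance specification.

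**Conclusion.** The concern holds as a conditional one about error bars. Read naturally, the plan gives too small a standard error and too narrow a CI for both Week 52 EASI percent-change contrasts whenever withdrawal placebo fails moderately more often than lebrikizumab. For assumed failure shares of 5-15% vs 20-50%, coverage is about 85-93% with a joint fit and about 89-94% with pairwise fits. Across wider assumptions it runs from about 83% to 96%, with no shortfall when failure is equal. The figures rest on those shares and on continuing responders lying near -80 to -90%. The mechanism rests only on the set-to-baseline rule, the 2:2:1 allocation and a single residual variance. The likely effect on the confirmatory EMA decision is small; the effect on the reported interval is not.

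**What to change.** In SAP 6.1.3.1, with a matching line in 6.4.2.1:
- State whether the three maintenance arms are fitted jointly or in pairs.
- Specify, for the maintenance ANCOVA, either HC3 robust standard errors or arm-specific residual variances (PROC MIXED with REPEATED / GROUP=treatment and Satterthwaite or Kenward-Roger degrees of freedom).
- State that these are the standard errors passed to PROC MIANALYZE.

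This takes a sentence or two and a line of code, settled before the Week 52 lock and before the maintenance assignment is unblinded. The estimand, the hierarchy and the data collected do not change. The price is a wider interval when failure rates differ: in the worked example by 8.62/6.42 = 1.34, or 34%, at 5% vs 30%, and by 8.98/7.50 = 1.20, or 20%, at 10% vs 30%. When arm variances are equal the interval is almost unchanged.

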6.1.3.2. Maintenance Secondary Population

The number and percentage of patients achieving or maintaining a categorical efficacy and health outcome responses will be summarized by treatment group for all scheduled visits, including Week 52.

Selected continuous secondary efficacy and health outcomes measure score and change from baseline (or percent improvement) will be summarized by treatment group at all scheduled visits during Maintenance Period, including Week 52 using descriptive statistics (n, mean, SD, median, minimum, and maximum). No inferential statistics will be provided for this population.

6.1.3.3. Maintenance Escape Population

For Maintenance W16 Escape Population, the number and percentage of patients achieving or maintaining a categorical efficacy and health outcome responses will be summarized by treatment group for all scheduled visits, including Week 52. Selected continuous secondary efficacy and health outcomes measure score and change from baseline (or percent improvement) will be summarized by treatment group at all scheduled visits during Maintenance Period, including Week 52 using descriptive statistics (n, mean, SD, median, minimum, and maximum). No inferential statistics will be provided for this population.

For Maintenance W24-48 Escape Population who were treated with lebrikizumab 250 mg Q2W following loss of response (EASI-50 nonresponse), the number and percentage of patients regaining EASI-50 response or achieving EASI-75 will be summarized every 4 weeks after lebrikizumab 250 mg Q2W treatment. No inferential statistics will be provided for this population.

